5.1.1.3. BIVV001 Dosing and PK Profile Period

The BIVV001 dosing and PK profile period is defined as the period starting at the dose of BIVV001 and ending at the last BIVV001 PK sampling time point.

5.1.1.4. Safety Observation Period During Advate Treatment

The safety observation period during Advate treatment starts at the single dose administration of Advate and ends immediately prior to the single dose administration of BIVV001.

5.1.1.5. Safety Observation Period During BIVV001 Treatment

The safety observation period during BIVV001 treatment starts at the single dose administration of BIVV001 and ends at the 28-day visit or time of early withdrawal. Subjects may resume treatment with their pre-study FVIII product during the 28-day safety observation period after completing Visit 14 activities (which include the 14-day inhibitor test).

5.1.1.6. Safety Observation Period During Pre-study FVIII Product Use

The safety observation period during pre-study FVIII product use starts at the first dose of pre-study FVIII product during the BIVV001 Treatment Period and ends at the 28-day visit or time of early withdrawal.

5.1.1.7. Major Surgical Period

The major surgical period starts at the date and time of the major surgery and ends at the date and time that routine prophylaxis is resumed. If there is no record for routine prophylaxis after the date of major surgery, then the major surgical period will end at the hospital discharge date.

5.1.1.8. Study Day

Study day is defined as the number of days relative to the date of first dose of study drug and starts on Day 1. Study day will be calculated relative to the Advate dose date as well as the BIVV001 dose date.

Study day relative to the Advate dose will be calculated as (date of event – date of Advate administration + 1). If a repeat Advate dose is administered, study day relative to the Advate dose will be calculated based on the first Advate dose administered.

Study day relative to the BIVV001 dose will be calculated as (date of event – date of BIVV001 administration + 1).

For laboratory data, days from treatment is calculated as (sample collection date – date of Advate administration) for the Screening period; (sample collection date – date of Advate administration + 1) for the Advate treatment period; and (sample collection date – date of BIVV001 administration + 1) for the BIVV001 treatment period.

Incomplete dates will be imputed for the calculation of study days, unless specified otherwise:

- If missing day only, the start date will be imputed as the first day of the month, while the end date will be imputed as the last day of the month
- If missing day and month, the start date will be imputed as the first day of the year, while the end date will be imputed as the last day of the year

5.1.1.9. Baseline

Unless otherwise specified, baseline will be defined as the last non-missing measurement taken prior to the first dose of study drug (Advate or BIVV001).

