3. STUDY DESIGN

3.1. Overall Study Design

[figure not shown]
This is a Phase 1/2a, open-label, dose-escalation, multicenter study designed to evaluate the safety, tolerability, and PK of a single IV dose of BIVV001 in subjects with severe hemophilia A who have received at least 150 exposure days of prior FVIII treatment.

Approximately 18 male PTPs aged 18 to 65 years will be enrolled: approximately 8 subjects in the low-dose cohort (Advate 25 IU/kg and BIVV001 25 IU/kg) and approximately 10 subjects in a high-dose cohort (Advate 65 IU/kg and BIVV001 65 IU/kg).

Each subject will be dosed with Advate followed by a PK sampling period. Following a brief washout period, each subject will then be administered BIVV001 followed by a PK sampling period. Subjects will undergo safety observation for 28 days following the injection of BIVV001, including sample collection for inhibitor assessments 14 and 28 days after the injection of BIVV001. Subjects may resume treatment with their pre-study FVIII product during the 28-day observation period after completing Visit 14 activities (which include the 14-day inhibitor test). Only subjects with adequate samples for PK and inhibitor characterization following both Advate and BIVV001 dosing will be considered evaluable; additional subjects will be enrolled as needed to ensure that at least 6 subjects in the low-dose cohort and 8 subjects in the high-dose cohort provide evaluable PK and inhibitor data.

An independent Data Safety Monitoring Committee (DSMC) will evaluate the safety data from the study on an ongoing basis.

Figure 1: Study Schema

* Screening may be extended up to 120 days with prior Sponsor approval. If the Screening Period extends beyond 56 days, screening assessments must be repeated as specified in the protocol prior to dosing with Advate. Washout duration at least 96 hours (4 days) from the most recent FVIII dose (prestudy FVIII) for a conventional product, 120 hours (5 days) for an extended half-life FVIII product.

[figure not shown]
** Washout duration at least 72 hours (3 days) from the Advate dose for the BIVV001 low-dose cohort, and at least 96 hours (4 days) for the BIVV001 high-dose cohort.

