5.1.1. Definitions

5.1.1.1. Screening Period

The screening period starts after signing the study consent form and ends immediately prior to the first dose of Advate or BIVV001.

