9.2.1. Hematology and Chemistry

Hematology and chemistry data and change from baseline will be summarized over time using descriptive statistics for each drug and dose level group using the Safety Analysis Set. The data will also be presented in a listing using the Safety Analysis Set. A flag for lab results outside the reported normal range will be included in the listing. In addition, lab results that occur during a major surgical period will be flagged.

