9.2.3. Coagulation Parameters

Samples for coagulation parameters (PT, aPTT, D-dimer, international normalized ratio, thrombin-anti-thrombin, and prothrombin fragment 1.2, and vWF) will be collected at Screening, Visits 2 and 3 (pre-injection for Advate and 1, 6, and 24 hours post-injection), Visits 6 and 7 (pre-injection for BIVV001 and 1, 6, and 24 hours post-injection), Visit 14 (14 days post-injection for BIVV001), and at the End of Study/Early Termination Visit.

Hours from treatment will be calculated as the time elapsed from initiation of the Advate injection to sample collection for the Screening period and Advate treatment period or as the time elapsed from initiation of the BIVV001 injection to sample collection for the BIVV001 treatment period.

Coagulation data and change from baseline will be summarized over time using descriptive statistics for each drug and dose level group using the Safety Analysis Set. The data will also be presented in a data listing using the Safety Analysis Set.

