9.4. Vital Signs

Vital signs include blood pressure, pulse, respiratory rate, and oral temperature. Vital sign data and change from baseline will be summarized over time using descriptive statistics for each drug

and dose level using the Safety Analysis Set. The data will also be presented by dose level and subject in a data listing using the Safety Analysis Set.

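### Read literally, the single baseline rule in SAP 5.1.1.9 measures BIVV001-period changes from a pre-Advate value; baseline should be defined by period

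*SAP*

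**What the plan says.** SAP 5.1.1.9 contains the only general baseline rule: "baseline will be defined as the last non-missing measurement taken prior to the first dose of study drug (Advate or BIVV001". It leaves room for exceptions elsewhere.

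Section 3.1 fixes the order of treatment: "Each subject will be dosed with Advate followed by a PK sampling period". BIVV001 follows in the same subject after a washout of at least 72 hours (low dose) or 96 hours (high dose) from the Advate dose.

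Three sections then call for changes from baseline by drug, and none states a different baseline:

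- Section 9.2.1: "Hematology and chemistry data and change from baseline will be summarized over time using descriptive statistics for each drug and dose level group".
- Section 9.2.3: "Coagulation data and change from baseline will be summarized over time using descriptive statistics for each drug and dose level group".
- Section 9.4: "Vital sign data and change from baseline will be summarized over time using descriptive statistics for each drug" and dose level.

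For coagulation, Section 9.2.3 also schedules samples at "Visits 6 and 7 (pre-injection for BIVV001 and 1, 6, and 24 hours post-injection", so a value taken just before BIVV001 is planned. It is not named as the reference for the post-BIVV001 samples.

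**The concern.** In a fixed-sequence study where everyone is to receive Advate first, the first study-drug dose is the Advate dose. Applied as written, the rule gives each subject one baseline, before Advate, and uses it for the tables headed Advate and for those headed BIVV001.

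Whatever happens to a measurement between the two pre-dose time points is then counted as part of the BIVV001 change: a lasting Advate effect, a bleed, repeated sampling or ordinary drift. A shift in one direction adds to an apparent BIVV001 effect, and a shift in the other hides part of a real one.

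This sits oddly with the rest of the SAP, which works by period. Section 5.1.1.8 sets separate Advate and BIVV001 clocks for study day, Sections 5.1.1.4 and 5.1.1.5 define separate safety periods, and Section 9.1 assigns adverse events by period. Baseline has no such rule. Two programmers could derive different BIVV001 changes from the same data, each with a defensible reading of 5.1.1.9.

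**Working it through.** The SAP states no figure for this point, so there is nothing to reproduce. The check is a trace through the text, an identity, and a rough size for carry-over.

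**1. Which value is baseline.** The rule in 5.1.1.9 looks back from the first study-drug dose. By Section 3.1 that dose is Advate for every subject. Sections 9.2.1, 9.2.3 and 9.4 do not use the permitted exception. The literal baseline is therefore the pre-Advate value for both periods.

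**2. What the BIVV001 change then contains.** Let B0 be the last value before Advate, B1 the last value before BIVV001, and Y a value after BIVV001. For a subject with all three,

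Y − B0 = (Y − B1) + (B1 − B0).

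The same holds for means when the same subjects contribute all three values. The second term is complete before BIVV001 is given. With a period baseline the change is Y − B1, and the second term drops out.

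**3. Where the SAP shows that B1 exists.** Among the change-from-baseline analyses, only coagulation has a stated pre-BIVV001 sample (Visit 6). Section 9.2 refers to the protocol for laboratory timing, and Section 9.4 gives no vital-sign schedule. Urinalysis is listed only (Section 9.2.2) and is not affected.

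**4. How far apart B0 and B1 are.** From the washout minima, at least 72 h (3 days) in the low-dose cohort and 96 h (4 days) in the high-dose cohort. If the Visit 2 value is missing, B0 falls back to Screening. That can be weeks earlier, since Section 3.1 requires repeat screening assessments only beyond 56 days.

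**5. Direct Advate carry-over.** Residual fraction of peak = 2^(−washout / half-life). Half-life (8 to 20 h) and recovery (2.0 to 2.5 IU/dL per IU/kg) are assumptions, not SAP figures. Residual activity = dose × recovery × fraction.

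| Cohort | Washout | Half-life | Fraction left | Residual FVIII (IU/dL) |
|---|---|---|---|---|
| 25 IU/kg | 72 h | 8 h | 0.0020 | 0.10 to 0.12 |
| 25 IU/kg | 72 h | 12 h | 0.0156 | 0.78 to 0.98 |
| 25 IU/kg | 72 h | 20 h | 0.0825 | 4.12 to 5.15 |
| 65 IU/kg | 96 h | 8 h | 0.0002 | 0.03 to 0.04 |
| 65 IU/kg | 96 h | 12 h | 0.0039 | 0.51 to 0.63 |
| 65 IU/kg | 96 h | 20 h | 0.0359 | 4.67 to 5.83 |

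These are FVIII activities. The SAP gives nothing that would turn them into a shift in aPTT or another marker.

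**6. Influence of one subject.** With about 8 or 10 subjects per cohort, one subject's B1 − B0 moves the mean by 1/8 or 1/10 of that amount. This is true of any mean and does not size the shift.

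**The case against.** **The wording may be meant per drug.** Section 5.1.1.8 also speaks of a first study-drug dose and then gives one rule per drug. It foresees a repeat Advate dose, so the word first would still serve a purpose under a per-drug baseline. In the other direction, Section 5.1.1.1 says screening "ends immediately prior to the first dose of Advate or BIVV001", which is one time point per subject, though that wording is not identical and defines something else. This objection stands to the extent that the intent is uncertain. It does not remove the problem, because 5.1.1.9 never states the per-drug rule that 5.1.1.8 does state.

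**A pre-study reference is legitimate.** Change from pre-study status is a reasonable descriptive quantity. In the low-dose cohort the pre-Advate value may even be the cleaner one: the minimum washout is 96 or 120 h from pre-study FVIII before Advate, against 72 h from Advate before BIVV001. This is a good reason to keep the pre-Advate change as a second display. It is not a reason to make it the only change shown under BIVV001.

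**The shift would be visible.** Observed values are summarized over time and listed, so the Visit 6 coagulation value will be reported. This is true and lowers the stakes. However, the spread of the within-period changes cannot be recovered from separate summaries.

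**The primary endpoints are not touched directly.** They are the occurrence of adverse events and of clinically significant laboratory abnormalities, including inhibitors. Neither is defined as a change from baseline, and no hypothesis is tested. This stands in full.

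**Conclusion.** The literal rule measures BIVV001-period changes from before Advate, and on the kinder reading the rule is ambiguous. Either way 5.1.1.9 needs a correction before analysis. The consequence is demonstrated for coagulation. For hematology, chemistry and vital signs it depends on a pre-BIVV001 value being collected, which this document does not show.

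The size of the pre-Advate to pre-BIVV001 shift is unknown. Direct Advate carry-over is probably small, on the assumed half-lives and recovery, but the shift can also come from bleeds, sampling or drift.

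A reader might infer more than the SAP supports:

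- That every BIVV001 mean change is biased by exactly the Visit 2 to Visit 6 shift. This needs paired pre-dose samples for every measure.
- That the tables will mix substantial effects of both drugs. The carry-over range does not suggest this.
- That particular thrombosis markers are bound to be affected because they respond to FVIII dosing. The SAP says nothing on this.
- That the primary safety assessment is compromised. Its endpoints do not use change from baseline.

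**What to change.** In 5.1.1.9, define baseline by period for the by-drug change summaries:

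- **Advate period:** the last non-missing value before Advate.
- **BIVV001 period:** the last non-missing value before BIVV001. For coagulation this is the Visit 6 pre-injection value. For hematology, chemistry and vital signs it applies where a pre-BIVV001 value is collected.

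Keep change from the pre-Advate value as a supplementary display, labelled as such.

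The new text should also say what happens when the pre-BIVV001 value is missing or not scheduled. For coagulation, the last value before BIVV001 could otherwise be the 24-hour post-Advate sample, which is a poor reference.

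The cost is one sentence for the core rule, a short addition for missing values, and one derived flag per period. No new data are needed and no figure in the SAP changes.

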5.1.1.10. Visit Windows

It is expected that all visits will occur according to the protocol schedule of assessments. All data will be tabulated per the evaluation visit as recorded on the electronic case report form (eCRF) even if the assessment is outside of the window for that study visit. Unscheduled visits will be included in data listings, but no assignment to a study visit will be made for the purpose of summary tabulations.

In the occurrence of repeat assessments within the same visit window, the last evaluation will be used for analysis.

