2.2. Study Endpoints

2.2.1. Primary Endpoint

The primary endpoints are as follows:

- The occurrence of adverse events (AEs)
- The occurrence of clinically significant abnormalities in laboratory tests, including development of inhibitors (neutralizing antibodies directed against FVIII) as determined by the Nijmegen-modified Bethesda assay

Details of the analysis of primary endpoints are described in [Section 9](#).

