5.1. General Principles

In general, the following approaches will be used in the analysis and summary of safety and PK endpoints, unless otherwise specified in this SAP.

Safety and PK data will be summarized using standard summary statistics for continuous and categorical data. Data will be summarized by study drug and dose level.

Data collected at unscheduled visits will be excluded from analysis, unless otherwise specified. However, all analysis data, including data collected at unscheduled visits, will be listed in the subject data listings.

No statistical hypothesis testing is planned.

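### A repeat within a visit window overwrites the earlier value, and unscheduled results reach no laboratory or vital-sign table, so a transient abnormality can be missing from every such summary

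*SAP*

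**What the plan says.** Two general rules decide which records enter the summaries.

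- **Repeats.** SAP 5.1.1.10: "In the occurrence of repeat assessments within the same visit window, the last evaluation will be used for analysis". The rule covers all data types.
- **Unscheduled visits.** SAP 5.1: "Data collected at unscheduled visits will be excluded from analysis, unless otherwise specified". SAP 5.1.1.10 adds: "Unscheduled visits will be included in data listings, but no assignment to a study visit will be made for the purpose of summary tabulations".

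The raw data are kept. SAP 5.1 says that "all analysis data, including data collected at unscheduled visits, will be listed in the subject data listings", and for hematology and chemistry 9.2.1 says: "A flag for lab results outside the reported normal range will be included in the listing". Section 9.2.2 has the same flag for urinalysis, which is listed only.

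The tables themselves are by visit. SAP 9.2.1: "Hematology and chemistry data and change from baseline will be summarized over time using descriptive statistics for each drug and dose level group". Sections 9.2.3 (coagulation) and 9.4 (vital signs) are worded alike, and 5.2.1 sets the statistics as n, mean, SD, median, minimum and maximum.

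SAP 2.2.1 names as a primary endpoint: "The occurrence of clinically significant abnormalities in laboratory tests, including development of inhibitors".

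**The concern.** The endpoint in 2.2.1 is an occurrence. It asks whether a clinically significant abnormality happened at any time, and a later normal value does not undo that. The planned tables answer a different question, namely what the selected value was at each visit.

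The selection can also depend on the result. An unexpected value is one reason to repeat a test, and where the repeat is closer to normal, keeping the last value moves the table in the reassuring direction. A transient deviation caught only between planned visits is not tabulated at all.

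This is a first-in-human study with safety as its primary objective and cohorts of about 8 and 10, so a single subject's value can change the mean and the maximum of a table.

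**Working it through.** The SAP gives no figure for this point, so there is nothing to reproduce. The check has two parts.

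**1. Where each kind of result ends up**

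| Situation | Rule | By-visit table shows | Abnormal value appears in |
|---|---|---|---|
| Abnormal scheduled value, repeat recorded under the same visit | 5.1.1.10, last evaluation | the repeat | listing only |
| Abnormal scheduled value, recheck recorded as unscheduled | 5.1 and 5.1.1.10, unscheduled excluded | the abnormal value | table and listing |
| Peak first found at an unscheduled visit | 5.1 and 5.1.1.10, unscheduled excluded | scheduled values only | listing only |
| Unscheduled recheck whose date falls inside a visit window | not stated which rule governs | not determined | listing; table depends on the reading |

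In every row an abnormality reported as an adverse event also enters the tables of 9.1.

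The first and third rows are the losses. They arise from different rules. In the second row the unscheduled rule keeps the abnormal value in the table. The fourth row is a gap in 5.1.1.10: data are tabulated by the visit recorded on the eCRF, but the repeat rule is worded in terms of the visit window.

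Sections 9.2.1, 9.2.3 and 9.4 state no exception to either rule. The table list in 12.1 has hematology, chemistry, coagulation and vital-sign summaries plus inhibitor and antibody status. It has no worst-value, shift or abnormality-count table.

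**2. Illustration of size (laboratory values assumed, not from the SAP)**

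Inputs: cohort sizes n = 8 and n = 10 from SAP 3.1. Assumed: upper limit 40; one subject with a first value x of 80, 120 or 200 and a same-visit repeat y = 30; the other n − 1 subjects evenly spaced from 15 to 40, so their mean is 27.5.

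Visit mean = [27.5(n − 1) + retained value]/n, so replacing x by y lowers the mean by (x − y)/n.

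- n = 8, last value kept: (192.5 + 30)/8 = 27.8; maximum 40; 0/8 above 40.
- n = 8, first value kept: (192.5 + x)/8 = 34.1, 39.1 or 49.1; maximum 80, 120 or 200; 1/8 (12.5%) above 40. Difference in means: 50/8 = 6.25, 90/8 = 11.25 or 170/8 = 21.25.
- n = 10, last value kept: (247.5 + 30)/10 = 27.8; maximum 40; 0/10.
- n = 10, first value kept: (247.5 + x)/10 = 32.8, 36.8 or 44.8; maximum 80, 120 or 200; 1/10 (10.0%). Difference in means: 5.0, 9.0 or 17.0.

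For a peak found only at an unscheduled visit, with 30 at the scheduled visits, the tables match the last-value lines. The visit mean is then correct for that visit, and what is missing is the extreme.

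**The case against.** The strongest reply is that little is lost. All values are listed, with out-of-range flags for hematology, chemistry and urinalysis. The DSMC reviews listings as well as summaries (3.5). With about 8 and 10 subjects and no hypothesis test, a reader can find one abnormal result in a listing. An abnormality reported as an adverse event enters the tables of 9.1 whichever value is kept by visit. Inhibitors, the named part of the laboratory endpoint, have their own confirmation rule (9.2) and count (9.2.4). All of this stands, and it limits the weight of the point. It does not supply a laboratory or vital-sign table that shows the abnormality. The adverse event route depends on the event being reported, and 9.2.3 and 9.4 mention no out-of-range flag in their listings.

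The reply also says that a last-value rule is a prespecified convention and not an error. The SAP does not say why tests are repeated or how rechecks are recorded. A repeat may follow an unusable sample, and if values are rising the last one is the worse one. This stands too, so the choice of first or last value for by-visit statistics is left open here.

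A reader might infer that the two rules together remove any abnormal result that prompted a recheck. The text does not support that: a recheck recorded as unscheduled is itself excluded and the abnormal scheduled value stays. Nor does it support saying that abnormal data are discarded from the study record.

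**Conclusion.** The point holds for the summary tables, within limits. A repeat recorded in the same visit window replaces an earlier abnormal value in the hematology, chemistry, coagulation and vital-sign summaries. Separately, a peak first found at an unscheduled visit enters none of them. No planned laboratory or vital-sign table recovers either, although 2.2.1 makes the occurrence of clinically significant laboratory abnormalities a primary endpoint.

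In the assumed example one subject's replaced value moves a visit mean by 6.25 to 21.25 units at n = 8 and by 5.0 to 17.0 at n = 10, and takes the abnormal count from 1 to 0. These figures show what one such case does, not how often it will happen. The size in practice depends on how many repeats are recorded under the same visit and on whether they lie closer to normal, neither of which the SAP gives. Urinalysis, which is listed only, and the inhibitor confirmation rule are not affected. The amendment should be made, since it needs no new data.

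**What to change.** - In 9.2.1, 9.2.3 and 9.4, add the worst post-dose value in the direction of concern (lowest and highest where both matter) per drug period and dose level, using the periods of 5.1.1.4 and 5.1.1.5. Take it over all scheduled, repeat and unscheduled valid results, and state it as an exception to 5.1 and 5.1.1.10. The listing-only treatment of laboratory results in a surgical period (9.2) can stay.
- In 5.1.1.10, state which rule governs an unscheduled recheck that falls inside a visit window.
- The by-visit convention, first or last value, may stay at the sponsor's choice.

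**Cost.** SAP wording and one extra row per table, from data already collected. The extremes will look less favourable, and subjects measured more often have more chances of an extreme. The drug periods are unequal: BIVV001 is followed to the 28-day visit, Advate only until the BIVV001 dose, which may come as early as 72 hours (low dose) or 96 hours (high dose) after Advate. A footnote should say that worst values are not to be compared directly between drugs.
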